3.2 CLINICAL LABORATORY EVALUATION

3.2.1 Available data

Per protocol, the following safety laboratory parameters are expected to be collected at Screening, at Day 1 pre-dose, at Day 2, 7, 14, 28, 56 and 84:

- Biochemistry: creatinine, urea, aspartate aminotransferase, alanine aminotransferase, gamma-glutamyl transpeptidase, total bilirubin, alkaline phosphatase, sodium, potassium, chlorine, and fasting glucose.
- Haematology: red blood cells count, white blood cells count and differential (neutrophils, eosinophils, lymphocytes, monocytes, basophils; % and values), total haemoglobin, haematocrit, and platelets count.
- Urinalysis (at Screening only): quantitative (proteins) and urinalysis – qualitative (ketones, microscopic examination of the sediment), will only be listed.
- Serum and urine pregnancy test and FSH (at Screening, Day 1, Day 28, Day 56, and Day 84 only), will only be listed.

Normal ranges are available as provided by the laboratory.

3.2.2 Derivation rules

Since not all the clinical sites involved in the study are able to provide WBC differential results but rather WBC absolute count results only, the WBC differential values at the given timepoint/assessment will be derived according to the following formula:

$$WBC \text{ type differential } (\%) = \left(\frac{WBC \text{ type } (count)}{WBC \text{ total } (count)} \right) * 100$$

where WBC types are: neutrophils, eosinophils, lymphocytes, monocytes and basophils.

Derived differential values will be used for analysis purposes, while observed differential values (when available) will be listed only.

The following abnormality categories will be defined:

- Low: value < lower limit of normal range;
- Normal: lower limit of normal range \leq value \leq upper limit of normal range;
- High: value > upper limit of normal range.

Notes:

- No normal ranges will be available for the derived WBC type differentials.

- Classification will be done in standardised units, by using non-imputed values and limits as reported in standardized units in the clinical database: a value $<X$ where X equals the lower limit of normal range will be classified as low. A value X with normal range $<X$ will be classified as high.
- If not straightforward how to categorize results, e.g. when results are reported as ranges, a worst-case approach will be used. A value of '4 to 6' with normal range '0 to 5' will thus be classified as normal for pre-dose assessments but as high for post-dose assessments.

3.2.3 *Presentation of results*

The statistical analysis will present results in standardised units.

Continuous laboratory parameters (biochemistry and haematology) will be summarised by means of descriptive statistics at each analysis visit by treatment. Actual values and changes from baseline will be tabulated. Categorical parameters will be listed only.

Laboratory abnormalities will be presented by treatment as cross-tabulations of the abnormality at each post-dose analysis visit and at the worst-case analysis visit versus the baseline abnormality.

All laboratory data will be listed.

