6.2.2 Baseline and change from baseline

The baseline value is the last non-missing value, including unscheduled assessments, before the administration of the study treatment. In case this results in more than one record with the same date and time, the unscheduled record is selected as baseline.

Note: decisions on whether a different baseline should be used in the analysis will be fully documented in the DRR.

Change from baseline is defined as:

Change from baseline at time point t = value at time point t – baseline value.

Relative change from baseline at time point t is defined as follows:

- When baseline value is not zero: $100*((\text{value at time point t} - \text{baseline value}) / \text{baseline value})$
- When both baseline value and value at time point t are zero: not calculated
- When baseline value is zero and value at time point t is not zero: not calculated

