6.3.3 Values below or above a threshold

Safety values expressed as below (or above) the limit of quantification will be imputed by the value of the quantification limit itself. Listings will always show the non-imputed values.

PK concentrations below the quantification limit will be flagged as BLQ in the concentration and parameters tables. All BLQ values will be considered as 0.00 for PK and descriptive statistical analyses.

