14.3.1.6	Serious ADRs by System Organ Class and Preferred Term (Safety Set) Tabulation of the number and percentage of subjects with serious ADRs by MedDRA system organ class and preferred term. The number of events will also be shown.	SAF	AET003
14.3.1.7	Grade 3 or 4 TEAEs by System Organ Class and Preferred Term (Safety Set) Tabulation of the number and percentage of subjects with grade 3 or 4 TEAEs by MedDRA system organ class and preferred term. The number of events will also be shown.	SAF	AET003
14.3.1.8	TEAEs Leading to Study Treatment Discontinuation by System Organ Class and Preferred Term (Safety Set) Tabulation of the number and percentage of subjects with TEAEs leading to study treatment discontinuation by MedDRA system organ class and preferred term. The number of events will also be shown.	SAF	AET003
14.3.1.9	TEAEs Leading to Death by System Organ Class and Preferred Term (Safety Set) Tabulation of the number and percentage of subjects with TEAEs leading to death by MedDRA system organ class and preferred term. The number of events will also be shown.	SAF	AET003
LABORATORY DATA			
14.3.2.1	Haematology: Summary of Actual Values and Changes from Baseline (Safety Set) Descriptive statistics of haematology results and changes from baseline by treatment, parameter and analysis visit. Table sorted first by parameter, then by analysis visit. Each parameter will begin on a new page.	SAF	LBT001
14.3.2.2	Haematology: Shift from Baseline (Safety Set) [KFR] Shift table of the abnormality at each analysis visit versus the baseline abnormality per parameter. Each parameter will begin on a new page.	SAF	LBT005

	Statistical Analysis Plan		
CLI-10067AA1-01	Final Analysis	Final 1.0	of 30MAY2024

Number	Title	Analysis Set	TLFs Library Template Number
14.3.2.3	Biochemistry: Summary of Actual Values and Changes from Baseline (Safety Set) Descriptive statistics of biochemistry results and changes from baseline by treatment, parameter and analysis visit. Table sorted first by parameter, then by analysis visit. Each parameter will begin on a new page.	SAF	LBT001
14.3.2.4	Biochemistry: Shift from Baseline (Safety Set) [KFR] Shift table of the abnormality at each analysis visit versus the baseline abnormality per parameter. Each parameter will begin on a new page.	SAF	LBT005
VITAL SIGNS			

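### SAP 3.2.2 classes a laboratory result that straddles a normal limit as normal before dosing and abnormal after it, so an unchanged reported result is tabulated as a shift

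*SAP*

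**What the plan says.** SAP 3.2.2 defines Low, Normal and High against the laboratory's normal range, and classifies "by using non-imputed values and limits as reported in standardized units in the clinical database". A note settles two boundary cases: a result below X is low when X is the lower limit, and a result of X is high when the normal range is below X. The next note covers whatever remains: "If not straightforward how to categorize results, e.g. when results are reported as ranges, a worst-case approach will be used". Its example is a result of 4 to 6 against a range of 0 to 5, which "will thus be classified as normal for pre-dose assessments but as high for post-dose assessments".

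The categories are then used as follows.

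- SAP 6.2.2: "The baseline value is the last non-missing value, including unscheduled assessments, before the administration of the study treatment".
- SAP 3.2.3 presents "cross-tabulations of the abnormality at each post-dose analysis visit and at the worst-case analysis visit versus the baseline abnormality".
- SAP 9.1 describes Tables 14.3.2.2 (haematology) and 14.3.2.4 (biochemistry) as "Shift table of the abnormality at each analysis visit versus the baseline abnormality per parameter". Both are tagged as key first results.
- The SAP's Definition of Terms makes an abnormality treatment-emergent if it appears after baseline and was absent at baseline. Listings 16.2.8.1 to 16.2.8.4 flag these.
- SAP 6.3.3, for the numerical summaries: "Safety values expressed as below (or above) the limit of quantification will be imputed by the value of the quantification limit itself".

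Protocol 12.3.5.7 plans shift tables against the normal range and says nothing about a classification that depends on when the sample was taken.

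**The concern.** A shift table measures change, so its two axes need the same yardstick. Here the baseline axis takes the lenient reading of an ambiguous result and the post-dose axis takes the severe one. The same reported result, with the same limits, therefore lands off the diagonal. A baseline that may already have been abnormal is recorded as normal, and the subject appears newly abnormal after dosing.

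Safety and tolerability are the primary objective, the two tables are among the first results to be read, and each dose column holds six subjects. A single off-diagonal entry is conspicuous at that size.

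The trigger may be wider than literal ranges. Ranges are given only as an example, and classification uses non-imputed values, so a censored result stays censored. If X lies strictly inside the normal range, a result below X or above X is not settled by the boundary note and can fall to the worst-case rule.

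**Working it through.** **Inputs.** The result and range come from the SAP 3.2.2 example (4 to 6; 0 to 5). Post-dose laboratory visits are Days 2, 7, 14, 28, 56 and 84 (SAP 3.2.1), plus the worst-case visit (SAP 3.2.3 and 6.2.5). Group sizes are six per dose level, 3 × 6 = 18 active and 3 × 2 = 6 pooled placebo (SAP 1.3 and 6.4.2).

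**Step 1: reproduce the SAP's example.** The interval 4 to 6 overlaps both Normal (0 to 5) and High (above 5). Pre-dose it resolves to Normal and post-dose to High, as the SAP states.

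**Step 2: carry an unchanged result through the tables.** Suppose 4 to 6 is reported at baseline and at every later visit.

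| Rule | Baseline | Each of 6 visits | Worst case | Off-diagonal cells |
|---|---|---|---|---|
| SAP 3.2.2 | Normal | High | High | 7 of 7 |
| Resolve to normal both times | Normal | Normal | Normal | 0 of 7 |
| Resolve to abnormal both times | High | High | High | 0 of 7 |
| Separate category both times | Indeterminate | Indeterminate | Indeterminate | 0 of 7 |

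Under the SAP rule the abnormality was absent at baseline by classification, so the listings also flag it as treatment-emergent. No SAP rule exempts a post-dose result identical to baseline.

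**Step 3: censored results (assumed limits).** Take a result below 5, unchanged, with an assumed normal range of 3 to 20. It could be Low (under 3) or Normal (3 up to 5). Read under the worst-case note it is Normal pre-dose and Low post-dose. If 5 is a quantification limit, SAP 6.3.3 sets both values to 5, so the change from baseline is 5 − 5 = 0 while the shift table shows Normal to Low. This conflict with 6.3.3 concerns quantification limits only; it does not arise for a literal range such as 4 to 6.

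**Step 4: size per affected subject, with all subjects observed.** 1/6 = 16.7% of a dose column or of pooled placebo; 1/18 = 5.6% of CHF10067 Total.

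**Step 5: how often.** The documents give no rate. Let q be the assumed chance that a subject has an unchanged straddling result for a given parameter, independently between subjects. The chance of at least one unsupported shift among n subjects is 1 − (1 − q)^n.

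| Assumed q | n = 6 | n = 18 |
|---|---|---|
| 1% | 5.9% | 16.5% |
| 5% | 26.5% | 60.3% |
| 10% | 46.9% | 85.0% |
| 20% | 73.8% | 98.2% |

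For example, 1 − 0.95^6 = 1 − 0.735 = 26.5%. The table shows sensitivity to q and is not an estimate.

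**The case against.** The rule is a declared, prespecified convention. The SAP also uses worst-case allocation for adverse events and medications with incomplete dates, and here it can only overstate post-dose abnormality. It applies to every treatment group, the tables are descriptive and no test depends on them. That stands as a limit on the consequences. It does not justify the rule: assuming the worst is cautious for a single result, but opposite assumptions at the two ends of a comparison create a change that was not reported.

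Reach is uncertain. The only trigger the SAP names is a result reported as a range, and the documents show no such result in chemistry or haematology. The extension to censored results follows from the wording, but needs a reporting limit strictly inside the normal range, and no instance is shown. Urinalysis is unaffected (screening only, listed only), as are derived white-cell differentials, which have no normal ranges. All of this stands.

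Downstream effects are limited. The listings show non-imputed values, normal ranges and clinical significance, so a reader can see that a result did not change. Laboratory adverse events rest on the investigator's judgement (Protocol 10.3 and 10.8), and the explicit escalation criteria in Protocol 6.2.2.1 count adverse events. This also stands.

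A reader might go further and infer that every such shift is false. The documents do not support that: a subject could move from 4 to 6 and be reported as 4 to 6 both times. A reader might also infer a bias against active treatment. The rule creates no systematic difference between groups, although with six pooled placebo subjects a chance imbalance is possible. Finally, the shift tables do not themselves call a shift treatment-emergent; that label comes from the Definition of Terms and the listing flags.

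**Conclusion.** The point holds as a defect in a stated rule. For a result that straddles a limit, SAP 3.2.2 turns an unchanged report into a normal-to-abnormal entry in the key laboratory shift tables and a treatment-emergent flag in the listings. The entry is unsupported by the data, though not proven false.

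An unchanged straddling result affects all seven post-dose cells. One such subject moves a dose column or pooled placebo by 16.7 percentage points and CHF10067 Total by 5.6, assuming all subjects are observed. The mechanism follows from the SAP's own example, its baseline definition and its table specification, with no outside assumption. Frequency is unknown, and the reach to censored results depends on how the worst-case note is read. The change should be made because it is cheap and the tables are small, but nothing here shows that the trial's safety conclusions would alter.

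**What to change.** In SAP 3.2.2:

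1. Keep the existing notes for X equal to a limit.
2. Replace the time-dependent worst-case note with one rule used identically before and after dosing, preferably a separate indeterminate category on both axes of Tables 14.3.2.2 and 14.3.2.4.
3. State that an unchanged reported result with unchanged limits is neither counted as a shift nor flagged as treatment-emergent.
4. Say where the indeterminate category ranks when the worst-case visit is derived, for instance between normal and abnormal.

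Two remedies that look simpler should be avoided. Classifying a result below X at X itself would make it Normal when X is the lower limit, because the Normal category includes its limits; that contradicts the SAP's own correct note that such a result is low. Placing a range at its midpoint puts 4 to 6 at (4 + 6)/2 = 5, which is Normal, and could hide a real post-dose elevation.

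The cost is a short SAP edit, one more table category, a small programming change and the loss of a one-sided conservative convention. Raw results and normal ranges stay visible in the listings.

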12.3.5.7 Safety laboratory data

At each post-dose timepoint quantitative laboratory parameters will be summarised by treatment as absolute value and change from baseline using descriptive statistics and 95% CIs.

Shift tables from baseline to the minimum and the maximum post-dose value, with regards to normal range, will be presented by treatment.

Clinical Study Code No.: CLI-10067AA1-01	Version No.: 6.0
EUDRACT No.: 2022-001079-15	Date: 06 July 2023

Urinalysis parameters will be presented in the listings.

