3.4 ELECTROCARDIOGRAMS

3.4.1 *Available data*

The following electrocardiogram (ECG) parameters will be collected:

- Triplicate local 12-lead ECG at Screening: heart rate (HR), PR interval, QRS interval, QT interval, corrected QT interval (Fridericia) (QTcF) and the corresponding interpretation
- Local 12-lead single ECG at other visits: heart rate (HR), PR interval, QRS interval, QT interval, corrected QT interval (Fridericia) (QTcF) and the corresponding interpretation

ECGs will be performed at Screening visit, at pre-dose on Day 1, and Days 2, 7, 28, and 84 days post-dose and in case of early termination visit.

3.4.2 *Derivation rules*

Mean values of the triplicates will be calculated at Screening and rounded as detailed in section 6.3.4. Records belonging to the same triplicate will be identified using variable EGREFID. All records of the triplicate will be used to calculate the mean, even if less or more than the expected three. Throughout the analysis, including the derivation of baseline and abnormalities, the mean values will be used. Individual triplicate values will only be listed.

For QTcF interval (ms), the following abnormality categories are defined:

- Actual values:
 - Males:
 - > 450 ms
 - > 480 ms
 - > 500 ms
 - Females:
 - > 470 ms
 - > 500 ms
- Changes from baseline:
 - Increase from baseline >30 ms
 - Increase from baseline >60 ms

Note: The worst-case, as defined in section 6.2.5, is the highest value and associated change.

3.4.3 *Presentation of results*

Local safety 12-lead ECG parameters (HR, PR, QRS and QTcF) will be summarised by means of descriptive statistics at each analysis time point by treatment. Actual values (with their 95% CI) and changes from baseline (with their 90% CI) will be tabulated.

For QTcF, the number and percentage of subjects with abnormal actual values will be presented at each post-dose time point and at the worst-case post-baseline analysis visit by treatment.

For QTcF, the number and percentage of subjects with abnormal changes from baseline will be presented at each post-dose time point and at the worst-case analysis visit by treatment.

All ECG data will be listed.

Graphs of the mean changes from baseline over time will be prepared for the continuous ECG parameters by treatment. In addition, individual graphs of the changes from baseline over time will be presented by treatment.

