Per parameter and analysis window, the value closest to the target time will be used in analysis tables and figures, other values will only be listed. If more than one value is located at the same distance from the target, then the latest in time will be selected. The value latest in time will be identified using, in order of preference, the assessment time, the visit and time point label or the group identifier. Missing values are removed before the selection is made.

Partially missing assessment dates or times disabling allocation to analysis windows will not be imputed and thus these assessments will not be considered in the per-time point analysis, except for the derivation of the worst.

6.2.5 *Worst-case*

A worst-case analysis visit (presented in the analysis as ‘At Any Time Point’, or similar) will be created for parameters for which abnormalities are defined to summarise values considered as the worst-case.

The worst-case analysis visit will be derived within the treatment phase, including scheduled and unscheduled assessments as well as the early termination visit assessments. Only post-baseline assessments will be considered for the worst-case analysis visit.

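### The SAP replaces the protocol's minimum and maximum laboratory shifts with per-visit shifts plus one worst-case row of undefined direction, and does not list the change in Section 7.1

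*SAP*

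**What the plan says.** Protocol 12.3.5.7: "Shift tables from baseline to the minimum and the maximum post-dose value, with regards to normal range, will be presented by treatment". That is two any-time summaries per parameter, one for each direction.

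SAP 3.2.2 defines three laboratory categories. Low is below the normal range, Normal is within it, and the third is "High: value > upper limit of normal range". SAP 3.2.3 then plans cross-tabulations of these categories against baseline for every post-dose visit and, in one further row, "at the worst-case analysis visit versus the baseline abnormality".

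SAP 6.2.5 says that the worst-case visit "will be created for parameters for which abnormalities are defined to summarise values considered as the worst-case". On the records to use, it says: "The worst-case analysis visit will be derived within the treatment phase, including scheduled and unscheduled assessments as well as the early termination visit assessments". Values up to and including baseline do not count.

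The SAP states a worst-case direction only once, in 3.4.2 under the QTcF categories: "The worst-case, as defined in section 6.2.5, is the highest value and associated change". Section 3.2 has no matching note for laboratory data.

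SAP 9.1 describes tables 14.3.2.2 (haematology) and 14.3.2.4 (biochemistry) as shifts at each analysis visit and marks both as key first results. SAP 7.1 lists departures from the protocol on immunogenicity, oxygen saturation plots, spirometry limits of normal, placebo-corrected ECG, TG2 and presentation by dose level. It has no laboratory item.

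**The concern.** A minimum shift and a maximum shift together show, for each subject and parameter, whether the value ever went low and whether it ever went high. One worst-case category cannot show both. With three categories and no ranking of Low against High, the SAP leaves the choice to whoever programs the table.

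These tables serve the primary objective, safety and tolerability, with six subjects on active drug at each dose level. One subject is 1/6 = 16.7% of a dose group, so a single subject shown in the wrong direction visibly changes the any-time percentage.

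**Working it through.** The documents state no figure on this point, so there is nothing to reproduce. The check compares the texts, classifies example subjects and then gives an illustration of size.

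**1. What 6.2.5 settles.** It settles the phase (treatment), the records (scheduled, unscheduled, early termination) and the restriction to post-baseline values. It does not settle which value is chosen when a subject has a Low at one visit and a High at another. The worst-case note in 3.2.2 does not fill the gap: it classifies a single result reported as a range and does not choose between visits.

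**2. Example subjects.** Take an arbitrary normal range of 3.5 to 5.0 and six post-dose values per subject:
- Fall only: 4.2, 3.2, 3.9, 4.1, 4.0, 4.2
- Rise only: 4.2, 5.4, 4.4, 4.1, 4.0, 4.2
- Both: 4.2, 3.2, 4.4, 5.4, 4.0, 4.2

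| Subject | Protocol: minimum | Protocol: maximum | One row, highest value | One row, lowest value | One row, any out-of-range value |
|---|---|---|---|---|---|
| Fall only | Low | Normal | Normal | Low | Low |
| Rise only | Normal | High | High | Normal | High |
| Both | Low | High | High | Low | Low or High, not both |

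The three single-row rules disagree, and the SAP does not choose among them. None can show both directions for the third subject. The per-visit tables show every Low and High in this example.

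**3. Why per-visit counts do not replace the any-time shifts.** Three Low entries in a dose group of six, spread over three visits, may be one subject three times (1/6 = 16.7%) or three subjects once each (3/6 = 50%). The per-visit tables cannot separate these cases; a shift to the minimum can.

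**4. Unscheduled values.** SAP 6.2.4 leaves unscheduled assessments out of the analysis unless they serve as the screening value or fall under a time window. The windows in 6.2.4 cover PK, vital signs, oxygen saturation and systemic markers, not clinical chemistry or haematology. Unless the data review report reallocates it, an unscheduled post-dose laboratory result can reach the shift summary only through the worst-case row. Early termination visits keep their own label, so they do not depend on that row in the same way.

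**5. Illustration of size.** Inputs from the documents:
- 6 scheduled post-dose visits (Days 2, 7, 14, 28, 56, 84; SAP 3.2.1)
- 6 × 3 = 18 active subjects (SAP 1.2)
- 11 biochemistry + 10 haematology parameters = 21, leaving out the derived differentials, which have no normal ranges (SAP 3.2.1, 3.2.2)

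This gives 18 × 21 = 378 subject-parameter pairs. Assumptions: each value has chance q of Low and q of High, visits are independent, and every parameter has both limits.

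P(at least one Low and at least one High) = 1 − 2(1 − q)^6 + (1 − 2q)^6

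| q | Probability | Expected pairs of 378 |
|---|---|---|
| 1% | 0.0029 | 1.1 |
| 2.5% | 0.0170 | 6.4 |
| 5% | 0.0613 | 23.2 |

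These are pairs for which the any-time row must omit one direction under any single-row rule. The per-visit tables still show both.

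**The case against.** The strongest reply is that little is hidden. The sentence in SAP 3.2.3 that introduces the worst-case visit also plans Low/Normal/High at every post-dose visit, and tables 14.3.2.2 and 14.3.2.4 are described that way. SAP 9.2 adds full and abnormal-only listings with low/high flags. In a descriptive study of 24 subjects, a reader can find every value. All of this stands, and it confines the point to the any-time row and to unscheduled values.

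A reader might infer that the QTcF rule carries over, so that the highest value is used for laboratory data and every fall disappears. The documents do not support that. The note stands in the ECG section under the QTcF categories, and neither 3.2 nor 6.2.5 extends it. Blood pressure, which is also two-sided, has separate decrease and increase categories and no highest-value rule.

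It would also go too far to call the worst case undefined, since 6.2.5 fixes its period and records. What is missing is the direction.

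The reply does not answer two things: per-visit counts cannot give the number of subjects ever Low or ever High, and unscheduled results generally have no other route into the tables.

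**Conclusion.** The point holds within those limits. The SAP replaces a protocol analysis that separates the two directions with one whose any-time row has no stated direction, and 7.1 does not list the change, although it lists smaller ones such as added individual oxygen saturation plots.

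At scheduled visits no abnormality leaves the shift tables. The any-time row can carry only one direction per subject and parameter, and an unscheduled abnormal value may be absent from the shift summary altogether and appear only in listings.

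The range of 1.1 to 23.2 pairs out of 378 rests on assumed tail rates of 1% to 5% and on independent visits. Positive correlation between a subject's visits would lower it. It should not be read as a count of shifts lost from the tables. The actual effect depends on the rule that is programmed, which the SAP does not fix.

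**What to change.** In SAP 3.2.3 and 6.2.5, replace the single laboratory worst case with two any-time cross-tabulations per parameter: baseline category versus category of the post-dose minimum, and baseline category versus category of the post-dose maximum. Use the scheduled, unscheduled and early termination records that 6.2.5 already specifies. Keep the per-visit shifts.

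Name both any-time panels in the descriptions of tables 14.3.2.2 and 14.3.2.4. These now mention only each analysis visit, whereas the blood pressure and QTcF abnormality tables name their worst-case time point.

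This restores the protocol's analysis. If a single row is kept instead, 7.1 should declare and justify the change, and the SAP should state how Low and High are ranked.

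The cost is one extra panel in two existing tables, with no new data.
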